2.3.4 Summary of the Two Azole Control Design

On January 26, 2011 (4 months after initial publication of the voriconazole trial by Wingard *et al.*³), we initiated a survey of the 80 COG Transplant Centers in North America and Australia/New Zealand in order to determine local standard-of-care anti-fungal prophylaxis for patients undergoing alternative donor (unrelated or mismatched related) HCT. The response rate was 80%, similar to the 83% seen in a survey of COG centers regarding anti-infective prophylaxis in patients with AML.⁴⁸ We found that for patients undergoing unrelated donor HCT (including umbilical cord blood), 56% of centers continue to use fluconazole, while 28% of centers have adopted voriconazole, 11% of centers utilize an echinocandin, and 5% administer a lipid formulation of amphotericin B. The data were very similar for patients undergoing mismatch related donor HCT (57%, 27%, 8%, and 8%, respectively). These results indicate that the profound lack of data for this patient population has led to a clinical situation where there is no clear universal agent of choice. Despite the fact that some centers have already adopted an echinocandin as the prophylaxis of choice, fully 89% of respondents indicated that they would be willing to participate in a trial of an echinocandin vs. an azole (center choice of fluconazole or voriconazole), as we have proposed for this trial. Even if all of the non-responding centers refused to participate, this would still be 71% of COG Transplant Centers. Finally, centers willing to participate were asked which azole they would choose as the comparator, and interestingly the pediatric HCT community was split almost evenly between fluconazole (54%) and voriconazole (46%), further justifying our two-azole design.

Therefore, our study is designed so that the local institutions will be allowed to choose what their standard-of-care anti-fungal prophylactic azole is for the study population in question. This practical study design reflects the real-world situation in which different agents have been adopted by individual centers on the basis of insufficient data. Furthermore, this design mirrors the Phase III trial in which posaconazole was compared to either fluconazole or itraconazole (two agents with different spectrums of activity) in non-transplant patients with neutropenia.²² In other words, that highly influential study used a similar strategy of comparing posaconazole against agents with and without mold activity in order to optimize acceptability of the trial.

For patients undergoing allogeneic HCT, fluconazole's spectrum of activity is limited primarily to *Candida* spp. It has been demonstrated in two pivotal trials to be superior to placebo, but no patients under the age of 12 years were included in either trial.^{1,2} Therefore, while fluconazole has been adopted as the "gold standard" for prophylaxis, for young children this is not based on any data. Voriconazole has the attractive feature of possessing activity against *Aspergillus* spp., as well as certain fluconazole-resistant strains of *Candida*, however, with the small trade-off that it is potentially less effective than fluconazole against fluconazole-susceptible strains of *Candida*, where it is fungistatic, rather than fungicidal.^{4,3} More importantly, the pharmacokinetics of voriconazole are not simple. In adults and children over the age of 12 years (the subjects of most trials to date), voriconazole has non-linear properties with relatively well-established dosing regimens. Even in adults however, recent studies have called into question the "standard" dosing, and have proposed dosing based on serum drug levels due to ~25% of patients found to have extremely low voriconazole levels.^{4,5,49} Part of this variability may be due to polymorphisms of the gene encoding for CYP2C19, which can result in an increase or decrease in voriconazole metabolism.⁵ In children, the situation is even more problematic due to linear kinetics. In children between the ages of 2 and 12 years, the optimal dose may be 7 mg/kg twice daily,^{7,9} while in children < 2 years of age, it may be as high as 8.5 mg/kg/dose twice daily.⁸ However, none of these opinions regarding dosing and drug level monitoring have been universally-accepted, leading to a potential wide range of different treatment strategies and outcomes. Nevertheless, because of the advantage of voriconazole against *Aspergillus* spp., its use has been adopted for primary prophylaxis at many institutions, despite a paucity of data to support this practice.

In the only head-to-head prospective trial of fluconazole vs. voriconazole, although there was a trend towards less IFI in the voriconazole arm, the difference was not statistically significant ($P = .12$).³ Furthermore, while patients over two years of age were eligible for this trial, in reality the number of pediatric patients enrolled was very small ($n = 51$), and in fact, no patient under the age of 9 years was given fluconazole. Therefore, the best trial to date has not been able to demonstrate that there is a difference between using fluconazole or voriconazole for IFI prophylaxis, despite the theoretical reasons why they might be different. Consequently, this is the rationale for the comparator being either fluconazole or voriconazole. Also, no trial to date has proven what the optimal agent is for children, especially those less than 12 years of age.

Because of this lack of convincing data to support one azole over the other, when designing this trial, it was felt that forcing the local institutions to adopt one agent as their standard-of-care would likely lead to a significant degree of non-participation. This potential conflict was confirmed during informal polling of leading pediatric transplant physicians both on the COG Stem Cell Transplant Steering Committee and at the open sessions of the last several COG National Meetings. In contrast, the study design that we have proposed clearly has widespread support in the pediatric HCT community (89% of respondents indicating that they wished to participate in the trial). As noted above, this potential issue has been dealt with before in other trials, such as the non-blinded randomized comparison of posaconazole to the institutional choice of fluconazole or itraconazole, which led to its wide acceptance by the community.²²

3.0 STUDY ENROLLMENT PROCEDURES AND PATIENT ELIGIBILITY

3.1 Study Enrollment

3.1.1 Patient Registration

Prior to enrollment on this study, patients must be assigned a COG patient ID number. This number is obtained via the eRDE system once authorization for the release of protected health information (PHI) has been obtained. The COG patient ID number is used to identify the patient in all future interactions with COG. If you have problems with the registration, please refer to the online help.

In order for an institution to maintain COG membership requirements, every newly diagnosed patient needs to be offered participation in ACCRN07, *Protocol for the Enrollment on the Official COG Registry, The Childhood Cancer Research Network (CCRN)*.

A Biopathology Center (BPC) number will be assigned as part of the registration process. Each patient will be assigned only one BPC number per COG Patient ID. For additional information about the labeling of specimens please refer to the Pathology and/or Biology Guidelines in this protocol.

3.1.2 IRB Approval

Local IRB/REB approval of this study must be obtained by a site prior to enrolling patients. Sites must submit IRB/REB approvals to the NCI's Cancer Trials Support Unit (CTSU) Regulatory Office and allow 3 business days for processing. The submission must include a fax coversheet (or optional CTSU IRB Transmittal Sheet) and the IRB approval document(s). The CTSU IRB Certification Form may be submitted in lieu of the signed IRB approval letter. All CTSU forms can be located on the CTSU web page (<https://www.ctsu.org>). Any other regulatory documents needed for access to the study enrollment screens will be listed for the study on the CTSU Member's Website under the RSS Tab.

IRB/REB approval documents may be faxed ([name]),
Emailed ([contact]) or mailed to the CTSU Regulatory office.

When a site has a pending patient enrollment within the next 24 hours, this is considered a "Time of Need" registration. For Time of Need registrations, in addition to marking your submissions as 'URGENT' and faxing the regulatory documents, call the CTSU Regulatory Helpdesk at: [name]. For general (non-regulatory) questions call the CTSU General Helpdesk at: [name].

3.1.3 Study Enrollment

Patients may be enrolled on the study once all eligibility requirements for the study have been met. Study enrollment is accomplished by going to the Enrollment application in the RDE system. If you have problems with enrollment, refer to online help in the Applications area of the COG website.

3.1.4 Timing

Patients must be enrolled before protocol-directed antifungal prophylaxis begins. The date protocol-directed antifungal prophylaxis is projected to start must be no later than **five (5)** calendar days after the date of study enrollment.

All clinical and laboratory studies to determine eligibility must be performed within 7 days prior to enrollment unless otherwise indicated in the eligibility section below.

3.1.5 Inclusion of Women and Minorities

Both men and women of all races and ethnic groups are eligible for this study. To allow non-English speaking patients to participate in the study, bilingual health care services will be provided in the appropriate language.

3.1.6 Randomization

Randomization will take place at the time a patient is entered On Study via RDE. Patients will be assigned to either antifungal prophylaxis with caspofungin or antifungal prophylaxis with an azole (fluconazole or voriconazole). Randomization will be stratified by:

- Center choice of azole: fluconazole vs. voriconazole.
- Age: ≥ 12 years vs. < 12 years
- Type of transplant: Umbilical cord blood (UCB) donor vs. Non-UCB donor with ex vivo T-cell-depletion vs. Non-UCB donor with standard pharmacologic GVHD prophylaxis.

3.2 Patient Eligibility Criteria

Important note: The eligibility criteria listed below are interpreted literally and cannot be waived (per COG policy posted 5/11/01). All clinical and laboratory data required for determining eligibility of a patient enrolled on this trial must be available in the patient's medical/research record which will serve as the source document for verification at the time of audit.

All clinical and laboratory studies to determine eligibility must be performed within 7 days prior to enrollment unless otherwise indicated. Laboratory values used to assess eligibility must be no older than seven (7) days at the start of therapy. Laboratory tests need not be repeated if therapy starts within seven (7) days of obtaining labs to assess eligibility. If a post-enrollment lab value is outside the limits of eligibility, or laboratory values are > 7 days old, then the following laboratory evaluations must be re-checked within 48 hours prior to initiating therapy: bilirubin, ALT (SGPT) and serum creatinine. If the recheck is outside the limits of eligibility, the patient may not receive protocol therapy and will be considered off protocol therapy. See Section 7.1 for required studies to be obtained prior to starting protocol therapy.

INCLUSION CRITERIA

3.2.1 Age

For centers that will use fluconazole as the antifungal comparator:

Age ≥ 3 months and < 21 years.

For centers that will use voriconazole as the antifungal comparator:

Age ≥ 2 years and < 21 years.

3.2.2 Diagnosis

- The patient must be undergoing allogeneic HCT from any donor (including matched related) with any stem cell source for any underlying condition.

3.2.3 Performance Level

Patients must have a performance status corresponding to ECOG scores of 0, 1 or 2. Use Karnofsky for patients > 16 years of age and Lansky for patients ≤ 16 years of age.

See https://members.childrensoncologygroup.org/prot/reference_materials.asp under Standard Sections for Protocols.

3.2.4 Organ Function Requirements

3.2.4.1 Adequate Renal Function Defined As:

- Creatinine clearance or radioisotope GFR ≥ 70 mL/min/1.73 m² **or**
- A serum creatinine based on age/gender as follows:

| Age | Maximum Serum Creatinine (mg/dL) | |
|-----------------------|----------------------------------|--------|
| | Male | Female |
| 1 month to < 6 months | 0.4 | 0.4 |
| 6 months to < 1 year | 0.5 | 0.5 |
| 1 to < 2 years | 0.6 | 0.6 |
| 2 to < 6 years | 0.8 | 0.8 |
| 6 to < 10 years | 1 | 1 |
| 10 to < 13 years | 1.2 | 1.2 |
| 13 to < 16 years | 1.5 | 1.4 |
| ≥ 16 years | 1.7 | 1.4 |

The threshold creatinine values in this Table were derived from the Schwartz formula for estimating GFR⁵⁰ utilizing child length and stature data published by the CDC.

3.2.4.2 Adequate Liver Function Defined As:

- Total bilirubin < 2.5 mg/dL unless the increase in bilirubin is attributable to Gilbert’s Syndrome, and
- SGOT (AST) or SGPT (ALT) < 5X upper limit of normal (ULN) for age.

EXCLUSION CRITERIA

3.2.5 Within 90 days of enrollment:

- Patients with a proven or probable invasive mold infection are not eligible.
- Patients with an incompletely treated invasive yeast infection are not eligible.

Patients with an elevated galactomannan level (≥ 0.5 Index) within 30 days prior to time of enrollment (if performed) must have a full evaluation for invasive aspergillosis (including a negative chest CT scan) during that time period to be eligible for enrollment.

3.2.6 Patients receiving treatment for an IFI are not eligible.

3.2.7 Patients with a history of echinocandin or azole hypersensitivity are not eligible.

3.2.8 Female patients of childbearing potential are not eligible unless a negative pregnancy test result has been obtained.

3.2.9 Sexually active patients of reproductive potential are not eligible unless they have agreed to use an effective contraceptive method for the duration of their study participation.

3.2.10 Lactating females are not eligible unless they have agreed not to breastfeed their infants.

REGULATORY

3.2. 11 All patients and/or their parents or legal guardians must sign a written informed consent.

3.2. 12 All institutional, FDA, and NCI requirements for human studies must be met.

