4.1 Overview of Treatment Plan

This is a randomized open-label clinical trial designed to assess the efficacy of caspofungin for preventing IFI (including IA) compared to antifungal prophylaxis with an azole (fluconazole or voriconazole), the standard therapies used in most COG institutions as prophylaxis in patients undergoing HCT.

At the time of enrollment, the enrolling center will declare whether the comparator arm will be fluconazole or voriconazole based upon that institution's standard of care and the choice of comparator should remain constant for the duration of the study.

Patients who consent to participate in ACCL1131 will be randomly assigned to antifungal prophylaxis with either an azole or caspofungin. Treatment with any antifungal prophylaxis initiated prior to enrollment must be terminated prior to starting protocol-directed antifungal therapy. Protocol prophylaxis will be started within 24 hours of transplant (Day 0). Administration of antifungal prophylaxis will continue until (a) HCT Day +42; OR (b) Day of Hospital Discharge; OR (c) Patient meets any off-protocol criteria (Section 8.1). Following discontinuation of study medications, institutions may revert to local standard of care for post-graftment antifungal prophylaxis.

If other systemic antifungal therapy is initiated for empiric therapy or treatment of suspected infection, then protocol prophylaxis should be held and assigned prophylaxis should resume when other systemic antifungal therapy is discontinued if this occurs prior to Day +42, Day of Hospital Discharge, or at the time a patient is taken off-protocol therapy (see Section 8.1).

Fluconazole and voriconazole may be administered either intravenously (IV) or orally. Caspofungin is only available as an IV formulation.

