5.0 DOSE MODIFICATIONS FOR TOXICITIES

5.1 Impaired Renal Function

When estimating renal function for adjusting drug doses, use the Schwartz formula for patients < 18 years of age and the Cockcroft and Gault equation for patients ≥ 18 years of age.

Fluconazole:

| Creatinine clearance (mL/min/1.73m ²) | Percent of dose | Dose in mg/kg (max dose) | |
|--|--------------------------|---|--|
| | | ≥ 3 months to 17.99 years: | ≥ 18 years to 20.99 years: |
| > 50 | 100% | 12 mg/kg (max 400 mg) | 6 mg/kg (max 400 mg) |
| ≤ 50 (no dialysis) | 50% | 6 mg/kg (max 200 mg) | 3 mg/kg (max 200 mg) |
| Hemodialysis | 100% after each dialysis | 12 mg/kg (max 400 mg after each dialysis) | 6 mg/kg (max 400 mg after each dialysis) |

Voriconazole:

| Creatinine clearance (mL/min/1.73m ²) | Percent of dose | Dose in mg/kg (max dose) |
|--|---|--------------------------|
| > 50 | PO & IV: 100% | Per Section 4.2.3 |
| ≤ 50 (no dialysis) | PO: 100% IV: Switch patient to oral voriconazole* | Per Section 4.2.3 |
| Hemodialysis | PO: 100% after each dialysis Avoid IV dosage form* | Per Section 4.2.3 |

*Parenteral formulation of voriconazole contains the excipient sulfobutyl ether beta-cyclodextrin sodium which accumulates in patients with renal impairment, and can worsen renal impairment. If a patient with renal failure cannot take the oral formulation of voriconazole, then voriconazole should be held until either the renal failure or inability to tolerate oral medications improves, at which point it may be restarted.

Caspofungin:

Adjustment of the dose is not needed in the setting of impaired renal function. Caspofungin is not dialyzable and supplementation is not required following hemodialysis.

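### Read literally, the entry rule admits a child with one transaminase above 5x ULN, although the protocol holds either azole at that level, and the conditional pre-dose re-check leaves out AST

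*Combined protocol and SAP*

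**What the plan says.** **Entry.** Section 3.2.4.2 sets a bilirubin limit and, in addition, requires "SGOT (AST) or SGPT (ALT) < 5X upper limit of normal (ULN) for age". Section 3.2 states how the criteria are to be read: "The eligibility criteria listed below are interpreted literally and cannot be waived".

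**Pre-dose re-check.** Section 3.2 says that labs used for eligibility may be no more than seven days old when therapy starts. If a value after enrollment falls outside the limits, or the labs are older than seven days, certain tests "must be re-checked within 48 hours prior to initiating therapy: bilirubin, ALT (SGPT) and serum creatinine". The consequence follows: "If the recheck is outside the limits of eligibility, the patient may not receive protocol therapy".

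**On treatment.** Section 5.2 uses the same rule for fluconazole and voriconazole. The drug is held when ALT or AST is above 5x ULN, and one of the conditions for restarting is that ALT and AST are both below 2.5x ULN. The rule refers to patients who develop these abnormalities. For caspofungin, Section 5.2 adjusts or holds the dose by Child-Pugh score.

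**Monitoring.** Section 7.1 requires AST and ALT at baseline and twice weekly. The fluconazole and voriconazole delivery maps (Sections 4.2.2 and 4.2.4) schedule both enzymes on treatment Days 1 and 4.

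**The concern.** The entry limit and the azole hold level use the same figure, 5x ULN, but combine the two enzymes in opposite ways. Entry passes if one enzyme is acceptable. The hold applies if one enzyme is unacceptable. A child whose AST and ALT lie on different sides of 5x ULN therefore satisfies both rules: fit to enter, and at a level where an azole should not be given.

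What is at stake is exposing a child to an azole at a transaminase level the protocol itself treats as too high. Section 6.2 (fluconazole) and Section 6.3 (voriconazole) both list liver failure among the rare toxicities, and Section 6.2 lists raised ALT/AST as occasional, at 5 to 20 per 100. If sites instead hold the azole at once, the child has been randomized to a drug that cannot then be given.

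**Working it through.** No statistical formula applies. The check sets the entry rule (3.2.4.2), the azole hold rule (5.2) and the re-check (3.2) side by side for each combination of enzymes. It assumes that bilirubin and all other criteria are met.

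| AST | ALT | Entry as written (either < 5x) | Azole hold level (either > 5x) | Entry if both must be < 5x |
|---|---|---|---|---|
| < 5x | < 5x | eligible | not reached | eligible |
| > 5x | < 5x | eligible | reached | not eligible |
| < 5x | > 5x | eligible | reached | not eligible |
| > 5x | > 5x | not eligible | reached | not eligible |

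The two middle rows are the conflict. For example, with AST 6x and ALT 4x ULN, 4 < 5 meets the entry rule and 6 > 5 meets the hold rule. With the values exchanged the result is the same. The figures are illustrative.

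**Does the re-check catch these children?**

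1. It is conditional. If the labs are seven days old or less and no later value is out of limits, it does not take place.
2. It does not name AST. In the second row, a re-check of the listed tests would not measure the raised enzyme.
3. It bars therapy only when a value is outside the eligibility limits. Under *or*, one passing enzyme keeps the child inside them. In the third row ALT is re-measured and found high, but an AST below 5x still satisfies the criterion.

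Points 2 and 3 together show why neither edit is sufficient alone. Adding AST to the list while keeping *or* stops nobody who has one passing enzyme. Changing *or* while leaving AST off the list leaves a later rise in AST outside the re-check.

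**Does Section 5.2 settle it?** There are two readings, and both leave a problem:

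- If *develop* limits the rule to elevations that arise on treatment, the child starts the azole above 5x ULN and no stated pre-dose liver rule prevents it.
- If the rule also covers an elevation already present, the Day 1 labs trigger a hold as soon as prophylaxis is due, and the azole waits until both enzymes are below 2.5x ULN.

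**Are the arms treated alike?** No. The Child-Pugh components in Section 5.2 are bilirubin, albumin, INR, ascites and encephalopathy. None is a transaminase, so the same child on caspofungin would not be held on this ground.

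**The case against.** The best case for leaving the text alone has four parts.

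*One enzyme may have been meant to suffice.* A re-check of ALT alone fits that design, and if ALT is the qualifying enzyme the re-check is complete. This stands as a possible intent, and the documents do not show that the sponsor meant *and*. But it does not remove the mismatch with Section 5.2, which acts on either enzyme. Section 5.2 also writes *and* when both enzymes must pass.

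*Entry limits and toxicity limits serve different purposes.* They need not match, particularly if Section 5.2 concerns only new elevations. That is fair as a general principle, and it makes an outright contradiction too strong a description. It still leaves a child starting an azole at a level where the same drug would be withheld a few days later.

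*AST is watched.* Baseline labs precede therapy, and both enzymes are due on treatment Days 1 and 4. A reader might infer that a raised AST would go unseen, and the schedule does not support that. Any exposure would be observed, and if the hold is applied it would be short. The physician can also stop protocol therapy under Section 8.1(d). That is general discretion, not a liver rule.

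*The age of the AST value.* Section 3.1.4 allows eligibility tests that "must be performed within 7 days prior to enrollment unless otherwise indicated in the eligibility section below" and a projected start up to five "calendar days after the date of study enrollment". A reader might add the two windows and conclude that a much older AST is acceptable at the first dose. Section 3.2 does not support this, because it caps eligibility labs at seven days when therapy starts. What remains is narrower: the remedy given for labs past that cap does not name AST, so the cap and the list fit poorly together.

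**Conclusion.** The point holds as a minor safety and consistency issue. It rests on the literal reading that Section 3.2 demands, and it survives either reading of *develop* in Section 5.2. On one reading a child starts an azole above the protocol's hold level. On the other, a child is randomized to an azole that must be held at once, with no matching transaminase hold on caspofungin.

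A reader might go further and infer that the difference between arms biases the comparison of fungal infection rates. The documents do not support that. A held child would stay in the azole arm under the intention-to-treat analysis in Section 9.3.4, but no baseline liver data are given. The number of children with one enzyme on each side of 5x ULN is unknown, and no effect on the primary result can be quantified.

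**What to change.** Make two wording changes together:

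1. In Section 3.2.4.2, require both AST and ALT to be below 5x ULN for age.
2. In Section 3.2, add AST to the tests re-checked within 48 hours before therapy.

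The cost is a protocol amendment. A few children with one enzyme at or above 5x ULN become ineligible; the documents give no basis for a count. A child with one enzyme at exactly 5x ULN would be excluded although the hold applies only above that level. The re-check gains one analyte on a draw already taken for bilirubin, ALT and creatinine. The sample size and the analysis plan do not change.

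If the sponsor did intend one enzyme to suffice, the protocol should say so and state in Section 5.2 what is to be done on Day 1 for a child who enters with the other enzyme above 5x ULN.
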